Aim 1: *To determine effects of dietary carbohydrate consumed (amount and type) on percent time with esophageal pH < 4.0, as well as number of reflux episodes, GERD symptoms and GERD medication use, in 200 obese veterans who have chronic high frequency of GERD symptoms.* To meet this aim we will use a randomized controlled trial in which we manipulate amount of total and simple dietary carbohydrate intake for duration of 9 weeks.

Aim 2: To assess associations between GERD resolution variables and factors related to potential mechanisms by which modifying dietary carbohydrate intake could resolve/reduce GERD in obese veterans.

2a: We will investigate associations related to whether the effect is nutritionally mediated by measuring change in dietary fiber load and dietary glycemic load, and thus, whether these changes are related to improved gastric acid secretion (% time pH < 4), gastric motility, and/or the other parameters that comprise the Johnson-DeMeester score.

2b: We will also investigate whether effects are associated with changes in the hormonal milieu by measuring hormonal response of gastrin, glucagon, GLP-1, ghrelin and insulin, which could potentially influence gastric acid secretion, gastric motility and/or lower esophageal sphincter function.

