 - **Hormones:** Serum gastrin will be assayed at LabCorp. Glucagon and GLP-1 by Luminex multiplex assay at the Diabetes Hormone core lab. Serum ghrelin (active acylated form) by radioimmunoassay at the Diabetes Hormone core lab. While several other hormones are involved in gastric acid secretion and motility, we have chosen two key stimulators (gastrin and glucagon) and two key inhibitors (GLP-1 and ghrelin), as well as insulin, to investigate in this proposal utilizing a dietary intervention in obesity.
- **Anthropometrics:**
 - **Height** (m) and **Weight** (kg) measured on calibrated digital equipment will be used to calculate **BMI**.
 - **Waist Circumference** will be measured using a flexible tape at the level of the umbilicus.⁴⁵
- **Body Composition:** In addition to total and regional body composition (fat, lean and bone mass) obtained from the Lunar iDXA (GE Healthcare), we will use new technology recently acquired by VICTR to estimate visceral adipose tissue (VAT) – a possible risk factor for GERD.⁴⁶ This fully automated approach to capture VAT has been validated against CT⁴⁷ and offers several advantages to MRI or CT: fast, low cost, exposes one to less radiation, and makes serial measurements possible.
- **Metabolic Testing:** To capture a more objective measure of change in energy balance due to the dietary intervention, we will perform indirect calorimetry by metabolic cart while subjects are at the CRC on week 1 and 9.
- **24 hour urine collection:** To effectively measure how well the body processes food intake
- **Dietary Intake:** will be assessed via averaging three 24-hour diet recalls obtained at baseline and again within a 7-day window of each clinical testing visit (study weeks 1 and 9). Recalls will be performed by the Vanderbilt Nutrition and Diet Assessment Core using the USDA multi-pass methodology,^{48,49} a standardized script, and computer-generated prompts (NDS-R, v. 2013, Nutrition Coordinating Center, Minn, MN). We are familiar with underreporting especially in people with high BMI and use portion size tools and statistical methods to assure

data reliability. The 1st of 3 recalls will be in-person at the CRC, which allows training of subjects in the interview methodology.

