analysis of only the complete cases would bias the results. *We will now request to subjects that inform of us they are dropping out between weeks 7 to 9 that they come in for a final visit. We have found that about 2/3 of subjects will agree to come in for a final visit even if they are not continuing to the end of study (week 9). This will significantly reduce the potential for missing data.* We will also attempt to obtain the specific reason for dropout on a case by case basis. Indirect information about the nonrandom dropouts will be obtained by using binary logistic models to predict the probability of dropping out using baseline variables. Thus, the impact of dropout on our results will be compared using assumptions that vary from missing completely at random to informative missing.

Sensitivity Analyses: We will use the daily diet data and daily medication checklist (type and amount) to conduct secondary analyses and verify the assumptions of our primary model. Summary statistics by diet group will be calculated to determine if weight loss, PPI use, total CHO, and simple CHO are consistent with the study design. We will also use the linear mixed effects model to determine if total and simple CHO are associated with total percent time < pH 4 by replacing the indicator variables in the primary model with these continuous covariates and their interaction. A secondary analysis of changes in PPI use over time will be considered. For this analysis, we will use the diary card data to create continuous variables of the weekly dose of PPI. PPI dose will be the outcome in a linear mixed effects regression model that includes time modeled flexibly using restricted and diet group indicators. An analogous model using weight as the outcome will be estimated. Our study is designed for subjects to maintain weight, but if weight loss differs by treatment arm, it may introduce confounding into our study. We will include weight loss as a covariate in our regression model to determine if our results are altered compared to the main analysis. This additional sensitivity analyses will be conducted as needed, for example where weight change is significantly different among groups, to assure effects are due to dietary not body weight change.

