Interpretation: Given our expertise in nutrition, metabolism and obesity ([name] and [name]), GERD ([name] and [name]), and GERD biostatistics ([name]), our group is ideally suited for executing and interpreting this study. We predict that we will uncover key diet related factors driving GERD symptoms and esophageal acid exposure in the obese Veteran, and we will develop a predictive risk model based on sound science. Physiologically, the proposed study will determine whether changes in several plausible gut hormones and/or improvement in insulin sensitivity is associated with the improvement in GERD with the dietary intervention.

Our preliminary data suggest that reduction of simple carbohydrate was most robustly associated with GERD resolution. The current study design will more rigorously address whether it is simple or total carbohydrate that is the driver of GERD symptoms and reflux. This has important implications for the development of more broadly disseminated dietary recommendations; a moderately high carbohydrate but low simple carbohydrate diet may be more tolerable to certain individuals than a low total carbohydrate approach. Conversely, if total carbohydrate is determined to be the major factor in the response, we will by definition be suggesting fairly high-fat and high-protein dietary intakes. Such approaches are increasingly recognized to have efficacy for weight loss as well as improvement in cardiometabolic parameters such as lipid profiles. Although dietary fat intake has been positively associated with GERD in obese subjects,⁵² the 4-5 investigations comparing effects of high fat to low fat diets on esophageal acid exposure and GERD symptoms have shown no worse outcomes with high fat diets.²⁰⁻²³ Certainly in metabolically at risk populations (such as obese Veterans) we would be conscientious

regarding the source and composition of dietary fat intake, as well as the protein load of the diet.

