The next level of analysis, for example, if lowering simple CHO intake reduces symptoms or esophageal acid exposure, will determine whether it is related to total dietary fiber intake or glycemic load. This analysis will reveal the extent to which “processing” of food ingredients contributes to GERD symptoms. The finding that higher dietary fiber and/or lower glycemic load is associated with less GERD would suggest that somewhat less of a focus on macronutrient composition (i.e., CHO vs fat) may be warranted, with more of a focus on consuming foods closer to their natural state.

Finally, by profiling several relevant gut hormones and assessing insulin sensitivity, we will investigate relationships for factors involved in plausible biological hypotheses for the effects of dietary carbohydrate on GERD symptoms. Our observation that reduction in simple CHO intake improves insulin sensitivity is consistent with a nutrient excess mechanism for insulin resistance. The mechanistic link between insulin sensitivity and GERD is most often considered in the context of weight loss, reduced waist circumference and improvement in abdominal pressures, and GERD symptoms. Here we investigate relationships that may suggest that improving insulin sensitivity independent of weight loss improves GERD. This has important implications for clinical translation, as induction of significant weight loss, and especially, long term maintenance of weight loss is a major clinical challenge. To reap clinical benefits on GERD and GERD symptoms without the requirement for weight loss would be a major clinical advantage. While gastrin release is not clearly understood to be differentially regulated by different macronutrients, GLP-1 and other gut hormones may well be. Thus, we will determine whether changes in the levels of any of the proposed gut hormones correlate with improvement in GERD. Identification of such an effect will drive specific hypotheses for future studies to uncover the mechanisms and clarify a mechanistic role in GERD response.

Thus, analysis of the data from the proposed study will determine which factor(s), fiber or glycemic load, total or simple carbohydrate, lower or higher fat in the context of more or less simple sugar, or gut hormones, should be targeted in next phase larger scale intervention studies. These findings will also drive the development of future experiments designed to understand the mechanistic effects of the optimal diet for GERD.

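### The Aim 2b association between insulin-sensitivity change and GERD change has no term for each subject's own weight change, so by itself it cannot support a weight-independent reading

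*Combined protocol and SAP*

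**What the plan says.** All references are to the combined protocol and SAP.

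- **The inference sought.** Section 10.0, Interpretation, says the link between insulin sensitivity and GERD is "most often considered in the context of weight loss, reduced waist circumference and improvement in abdominal pressures". It continues: "Here we investigate relationships that may suggest that improving insulin sensitivity independent of weight loss improves GERD". It then describes GERD benefit that does not depend on losing weight as a major clinical advantage.
- **The analysis offered.** Section 2.3 words Aim 2 as "To assess associations between GERD resolution variables and factors related to potential mechanisms", and Aim 2b will "investigate whether effects are associated with changes in the hormonal milieu", with insulin among the variables. Section 10.0, Interpretation, asks whether "improvement in insulin sensitivity is associated with the improvement in GERD with the dietary intervention", and for the hormones says "we will determine whether changes in the levels of any of the proposed gut hormones correlate with improvement in GERD". No model, covariate list or significance level is given for Aim 2.
- **Weight in the analysis.** Section 10.0, Sensitivity Analyses, adds weight loss to the regression model and compares the result with the main analysis, which is the diet-arm comparison of percent time with pH below 4. On when this is done: "This additional sensitivity analyses will be conducted as needed, for example where weight change is significantly different among groups".
- **Weight in the design and data.** Section 2.1 (Weight Loss) and section 2.2 (Diets) prescribe energy intake to hold weight steady and monitor weight and DEXA. Section 6.0, Measures, adds waist circumference and visceral fat, the latter described as "a possible risk factor for GERD".

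**The concern.** The plan itself names weight as the usual route connecting insulin sensitivity and reflux. A subject who happens to lose weight may improve on HOMA-IR and on acid exposure for that reason alone, and a subject who gains may worsen on both. The two changes are then correlated across subjects even if neither influences the other.

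Equal mean weight change across arms does not prevent this, because the association is between individuals and individuals drift in both directions within every arm. Arm indicators do not remove it either. A check triggered by a between-arm difference looks at the wrong source of variation for this question.

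What is at stake is the interpretation of a secondary, mechanistic aim. Section 10.0 says the findings will choose targets for the next, larger studies, so a correlation produced by weight could be carried forward as a weight-independent mechanism. The randomised comparison of diets on the primary outcome is not affected.

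**Working it through.** **1. Inputs.**
- Completers: 200 × 0.80 = 160, or 40 per arm (section 6.0, Randomization). This reproduces the plan's figure.
- Level: two-sided 0.05. Section 2.2 states it for the primary power analysis; using it for Aim 2 is an assumption.
- r1 = correlation of weight change with HOMA-IR change; r2 = correlation of weight change with pH change. The documents give neither, so a range is shown.
- The plan states no figure for Aim 2, so there is none to reproduce.

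**2. Model with no true link.** Let w be standardised weight change with the same mean in every arm. HOMA-IR change = r1·w + noise and pH change = r2·w + noise, with the two noises independent. The induced correlation between the two changes is r1 × r2.

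**3. Analytic check (Fisher z).** With √(160 − 3) = 12.53,

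Pr(reject) = Φ(12.53·atanh(r1·r2) − 1.96) + Φ(−12.53·atanh(r1·r2) − 1.96).

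Example, r1 = r2 = 0.3: induced r = 0.09; 12.53 × 0.0902 = 1.13; Φ(−0.83) + Φ(−3.09) ≈ 0.20.

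**4. Simulation.** 5,000 trials per row, 40 per arm, testing the HOMA-IR coefficient.

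| r1 / r2 | Induced r | Analytic | Arm-adjusted only | Arm + own weight change |
|---|---|---|---|---|
| 0.1 / 0.1 | 0.01 | 5.2% | 4.9% | 4.5% |
| 0.2 / 0.2 | 0.04 | 7.9% | 8.2% | 4.7% |
| 0.3 / 0.2 | 0.06 | 11.7% | 12.0% | 5.0% |
| 0.3 / 0.3 | 0.09 | 20.4% | 19.6% | 5.0% |
| 0.4 / 0.3 | 0.12 | 32.7% | 31.7% | 5.0% |
| 0.4 / 0.4 | 0.16 | 52.5% | 52.9% | 4.3% |

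The last column returns to about 5% by construction, because weight is the only shared cause in the simulation.

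**5. Would the existing check help if extended to Aim 2?** If weight were added only when a 0.05-level test found weight change to differ among arms, then with equal arm means it would be added in about 5% of trials. The false-positive rate would be 18.9% instead of 19.6% at 0.3/0.3, and 50.7% instead of 52.9% at 0.4/0.4.

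**6. Which values of r2 are plausible?** Section 2.2 gives SD 9.8 and intraclass correlation 0.39 for percent time with pH below 4. The SD of a subject's change is:
- 9.8 as total SD: 9.8 × √(2 × 0.61) = 10.8 points;
- 9.8 as residual SD: 9.8 × √2 = 13.9 points.

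The plan's power table is reproduced to within 2 points on the residual reading (for example 0.815 against the stated 0.80), but not on the total reading (0.96 to 0.99). Both are carried here. The shift in acid exposure per 1-SD weight change is r2 times that SD:

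| r2 | Shift (points) |
|---|---|
| 0.1 | 1.1 to 1.4 |
| 0.2 | 2.2 to 2.8 |
| 0.3 | 3.2 to 4.2 |
| 0.4 | 4.3 to 5.5 |

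The smallest diet effect in the power table is 3.7 points. With r2 = 0.1, the formula in step 3 gives about 7% when r1 = 0.3 and about 10% when r1 = 0.5.

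**7. Cost in precision.** The correlation detectable with 80% power is tanh((1.96 + 0.84)/12.53) ≈ 0.22. One or two further degrees of freedom out of about 160 leave this essentially unchanged.

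**The case against.** **The text is hedged.** A reader might infer that the plan sets out to prove a weight-independent mechanism as its main conclusion. The documents do not support that. The sentence speaks of relationships that may suggest such a link, in an Interpretation narrative aimed at later studies. This objection stands and limits the weight of the point.

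**The sensitivity analysis is broader than its example.** A reader might infer that weight adjustment happens only when arms differ. The text says as needed and gives a between-arm difference as an example, so the rule in step 5 is one reading, not the stated plan. This also stands. Even so, the analysis is defined against the main diet-arm model and is nowhere extended to Aim 2.

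**The size may be small.** A reader might infer that a false finding is more likely than not. That needs r1 and r2 of about 0.4 or more (88% at 0.5/0.5). By step 6, ordinary drift on weight-maintaining diets would then have to move acid exposure by more than the 3.7-point diet effect. The documents give no ground for assuming that. At 0.1 the inflation is nil and at 0.2 it is small.

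**No Aim 2 test is specified.** True: the 0.05 verdict and the arm-adjusted model are constructions used to show size. The whole Aim 2 model is unspecified, and the weight term is the part that the stated inference depends on.

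**Adjustment may over-correct if weight lies on the pathway.** This does not stand. The adjusted estimate is the one a weight-independence statement refers to, and reporting both estimates shows the difference.

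**Conclusion.** The point holds as a mismatch between an inference and the analysis described for it. An association of changes without the subject's own weight change cannot, whatever the size of the bias, distinguish a weight-independent link from a weight-driven one. Neither the weight-maintaining design nor the diet-arm sensitivity analysis fills that gap, because both leave within-arm variation in place.

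The magnitude is not established. Under the assumptions above (160 completers, 0.05 level, equal arm means, weight the only shared cause), the false-positive rate runs from nominal at correlations of 0.1, through about 8% at 0.2 and 20% at 0.3, to 53% at 0.4. The design favours the lower part of that range. The matter is confined to a secondary, hypothesis-generating aim. It is still worth correcting, because the plan names the confounder, already measures it, and intends to use the result to direct later trials.

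**What to change.** Add to section 10.0, for the Aim 2b analyses of HOMA-IR or insulin change against GERD change:

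- Always include diet arm and the subject's own weight change over the same interval, with no trigger.
- Report the estimate with and without the weight term.
- Optionally give a second version with DEXA total, truncal or visceral fat change, or waist change, in place of or alongside weight.
- Use weight-independence wording only for the adjusted estimate. State that it remains associational, since other shared causes such as dietary adherence may persist after adjustment.

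The cost is one line of analysis text and one or two degrees of freedom. Weight, waist and DEXA are already planned measures, so no new data collection is needed.

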- HTLS Diet: 55% total CHO (85% complex / 15% simple CHO), 30% fat, 15% protein
- LTHS Diet: 35% total CHO (½ complex / ½ simple CHO), 50% fat, 15% protein
- LTLS Diet: 35% total CHO (85% complex / 15% simple CHO), 50% fat, 15% protein

Power Analysis and Sample Size: Our primary outcome is a continuous variable, percent time pH < 4.0 in the 24hr period. This is based on the clinical gold standard of pH < 4.0 for > 5.5% of the 24hr period. To determine sample size, we used data from 205 obese patients with chronic GERD from [name] clinic population. In this sample, the SD for percent time < pH was 9.8 and the interclass correlation was 0.39 ($\omega = \omega^2_b / (\omega^2_b + \omega^2_e)$). We used these values as inputs into a statistical simulation (10,000 replications) to determine the probability of detecting any treatment group effect using the linear mixed effects model. The following table presents the power of an overall (4 d.f.) test to detect various absolute changes in pH by diet groups ($\omega_1, \omega_2, \omega_3, \omega_4$). We assume $n_1=40$ subjects per group complete the entire study and $n_2=5$ or $n_2=3$ subjects per group complete 80% of the study before returning for pH testing. We use a two-sided significance level of 0.05.

Absolute effect size	3.7%, 3.7%, 3.7%, 3.7%	0%, 4.5%, 4.5%, 4.5%	0%, 4%, 4%, 4%	0%, 0%, 5%, 5%	0%, 0%, 0%, 7%
Power ($n_1=40, n_2=5$)	0.80	0.89	0.80	0.85	0.87
Power ($n_1=40, n_2=3$)	0.79	0.88	0.79	0.83	0.86

Power for different effect size scenarios that give 80%-90% power are presented in the table. If the absolute change in percent time pH < 4 for each of the four diet groups is 3.7%, we will have 80% power to detect any effect of diet. If 1 diet group is not effective and the other groups have a 4.5% effect, we have almost 90% power to detect a diet effect. In our pilot data, the 25th/50th/75th percentiles of percent time pH < 4 were 4.8%/8.5%/12.4%. Thus, a 3.7% decrease is a change from the median to 25th percentile, a 4% decrease is a change from the 75th percentile to the median, a 5% decrease is a change from the 80th percentile to the median, and a 7.6% decrease is a change from the 75th to the 25th percentile. The standard error for any pairwise comparison between groups will be 1.9% under all scenarios ($n_1=40$ and $n_2=3$ or $n_2=5$).

2.3 SPECIFIC AIMS:

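### Aim 2 states no arm term for relating factor changes to GERD improvement, so where the same arms shift both, an unadjusted correlation can suggest a mechanism that is not there

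*Combined protocol and SAP*

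**What the plan says.** Aim 2 (Section 2.3) is "To assess associations between GERD resolution variables and factors related to potential mechanisms". Aim 2a asks "whether the effect is nutritionally mediated by measuring change in dietary fiber load and dietary glycemic load". Aim 2b looks at the hormonal milieu "by measuring hormonal response of gastrin, glucagon, GLP-1, ghrelin and insulin".

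The Interpretation part of Section 10.0 adds that "we will determine whether changes in the levels of any of the proposed gut hormones correlate with improvement in GERD". It also introduces the fiber and glycemic-load analysis as a next step, giving as its example the case where less simple carbohydrate has reduced symptoms or acid exposure.

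No Aim 2 model, covariate list, arm term or mediation method appears. The closest specified model relates total and simple carbohydrate to percent time with pH below 4. It appears in Section 2.1 and again under Sensitivity Analyses in Section 10.0, and it works "by replacing the indicator variables in the primary model with these continuous covariates and their interaction".

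Two uses of the results are stated. A hormone finding is a lead: "Identification of such an effect will drive specific hypotheses for future studies to uncover the mechanisms". The closing paragraph goes further: the analysis is to settle which factors, fiber, glycemic load and gut hormones among them, "should be targeted in next phase larger scale intervention studies".

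**The concern.** Randomized diet can change both reflux and a candidate factor. If it does so by separate routes, the two changes are still correlated when subjects from different arms are analysed together, because arm is a common cause. The association then reflects the diet contrast, not a link between the factor and reflux.

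The text, followed literally, yields such an association. Aim 2a's wording invites a reading as mediation, and Section 10.0 lets the result influence what the next, larger trials target. The example given for running the fiber and glycemic-load analysis is also the case in which arms differ on reflux, so the artefact could be active.

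**Working it through.** **Inputs.** Section 2.2 gives "the SD for percent time < pH was 9.8 and the interclass correlation was 0.39", 40 full completers per arm (160 in all), a two-sided 0.05 level, and effect scenarios that include 0/0/5/5 points. Section 6.0 gives 200 randomized and 20% dropout: 200 × 0.80 = 160. The documents give no power or error rate for Aim 2.

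**The plan's own figures.** The Section 10.0 mixed model (common baseline mean, random intercept, four arm-by-time effects, time 1 or 0.8) with a 4 d.f. test was used to recompute the power table.

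- With 9.8 as the residual SD, power for n2=5 is 0.815/0.895/0.802/0.859/0.883, against the stated 0.80/0.89/0.80/0.85/0.87. The table reproduces within 2 points.
- The stated pairwise standard error of 1.9 fits only with 9.8 as the total SD (1.94 for n2=5). The residual reading gives about 2.5.

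Both readings are therefore carried forward.

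**SD of the outcome change, s.**

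- Residual reading: 9.8 × √2 = 13.86.
- Total reading: 9.8 × √(2 × (1 − 0.39)) = 10.82.

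**Expected unadjusted correlation.** Let two of the four arms improve by 5 points and the same two shift the factor by d, in units of its within-arm SD of change. Assume no link between factor and reflux within any arm. The between-arm covariance is 5d/4 = 1.25d. The between-arm variances are 25/4 = 6.25 and d²/4. So

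r = 1.25d / √[(6.25 + s²)(1 + d²/4)],

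and the chance of p < 0.05 is about 1 − Φ(1.96 − atanh(r) × √157).

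Worked case, s = 13.86 and d = 1: r = 1.25 / √(198.33 × 1.25) = 0.079. Then atanh(r) × 12.53 = 1.00, and 1 − Φ(0.96) ≈ 0.17.

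**Simulated false-positive rates, 0/0/5/5, same arms shifted (40 per arm):**

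| Assumed factor shift | Unadjusted, s = 13.86 | Unadjusted, s = 10.82 | Arm in model |
|---|---|---|---|
| 0.3 SD | 6% | 7% | 5% |
| 0.6 SD | 10% | 13% | 5% |
| 1 SD | 17% | 24% | 5% |
| 2 SD | 36% | 53% | 5% |

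**Other scenarios from the power table, shift in the arms that improve.**

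- 0/4/4/4: 10-12% at 1 SD and 18-26% at 2 SD.
- 0/0/0/7: 19-27% at 1 SD and 42-62% at 2 SD.

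With arm in the model, the rate was 4.4-5.7% in every cell.

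**Where nothing happens.**

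- If all four arms improve by 3.7 points (the plan's first scenario), the between-arm covariance is zero and the rate stays near 5%.
- If reflux follows one diet dimension and the factor the other, say 0/0/5/5 with a shift of 0/d/0/d, the covariance is 5d/4 − 2.5 × d/2 = 0. The rate is again near 5%.

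**What shifts are plausible?** Table 2 of the preliminary data (Section 3.0) gives mean change ± SD at week 9, for subjects with and without GERD:

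- Glycemic load: 82.5/30.1 = 2.7 and 62.2/39.9 = 1.6 SD.
- HOMA-IR: 1.1/1.8 = 0.6 and 0.3/1.2 = 0.25 SD.
- Total fiber: 3.3/8.4 = 0.4 and 5.2/5.7 = 0.9 SD.

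These are uncontrolled changes on a single diet, not contrasts between these four arms, so they are indicative only. No shifts are given for the gut hormones.

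**The case against.** A reader might infer that the plan pools all subjects and ignores arm. The documents do not say so: an arm term is neither stated nor excluded. The weight-loss sensitivity analysis in Section 10.0 adds a covariate to the regression model and is not said to drop the arms. This stands. The supportable statement is that no arm term is given and that the nearest specified model for dietary factors removes the indicators.

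A reader might also infer that anything the diet moves will look like a mechanism. The numbers do not support that. The artefact needs arm differences in both factor and reflux, in overlapping arms. At the 0.3-0.6 SD seen for HOMA-IR in the pilot, the false-positive rate is only 6-13%. A shift near 2 SD has support for glycemic load alone. The diets set carbohydrate, fat and protein but no fiber target.

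The hormone work is framed as hypothesis-generating and does not touch the primary test. This also stands, and a formal multiplicity correction across the hormones would be a matter of preference. The framing does not cover Aim 2a's mediation wording or the choice of next-phase targets.

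Finally, adjusting for arm discards the randomized contrast. For glycemic load, much of what remains may be adherence variation and error in three averaged diet recalls, so a genuine mediator could show little. This is a real cost, but it reflects a limit of the design that an unadjusted correlation would conceal.

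**Conclusion.** The concern holds in a limited form. As worded, Aim 2 permits an association confounded by arm. When the diets differ on reflux and the same arms shift the factor, its false-positive rate is about 17-24% at a 1 SD shift and 36-53% at 2 SD, against 5% with arm in the model. These figures assume 160 completers, a 5-point effect in two arms, perfect alignment of the two patterns, no within-arm link, and factor shifts that the documents do not supply. Each range spans the two readings of the SD of 9.8.

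Glycemic load is the main case. For insulin resistance and fiber, the pilot suggests smaller inflation. For the gut hormones the size is unknown. Aim 1 is unaffected.

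**What to change.** In Section 10.0, specify each Aim 2 analysis as a regression of the change in the GERD measure on the change in the factor, with arm indicators and the baseline values of both. Report it beside the unadjusted correlation. Base mechanism wording and the choice of next-phase targets on the arm-adjusted result.

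Call the Aim 2 results exploratory, and align Aim 2a's mediation wording with that. State that within-arm associations may still be confounded, since the factors are not randomized within arm.

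The change is to SAP wording, plus one extra model per association; no new data are needed. Within-arm estimates are less precise. For a near-proxy of arm such as glycemic load they may be uninformative and attenuated by diet-recall error. The plan should say that such a result will be reported as the trial being unable to separate the factor from the diet, not as evidence against the factor.
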